9.2 Secondary Efficacy

The secondary efficacy analyses will be based on the ITT population, unless otherwise specified.

Table 8 provides an overview of the planned efficacy analyses.

As part of the overall efficacy evaluation, an exploratory analysis of platelet activation and morphology will be performed on platelets obtained from peripheral blood. The data from these analyses are captured outside the eCRF, and thus the reporting is not covered in this SAP.

Table 8 Overview of Planned Secondary Efficacy Analyses

Endpoint/Parameter/Display Type	Absolute ^[1]				Change from Baseline ^[1]			
	Summary		Individual		Summary		Individual	
	T	F	F	L	T	F	F	L
Longitudinal engraftment and WASP expression	X	X	X	X				
Multilineage Engraftment	X	X	X	X				
Frequency of Severe Infections	X	X			X	X		
Frequency of Bleeding episodes	X	X			X	X		
Autoimmunity phenomena ^[2]	X				X			
Eczema	X		X	X	X			
Quality of life: Social life Requirement of drugs Hospitalization	X		X	X				

T = Table, F = Figure, L = Listing, X = Display generated.

• Summary = Represents TF related to any summaries (i.e. descriptive statistics) of the observed raw data.

• Individual = Represents FL related to any displays of individual subject observed raw data.

^[1] Absolute and change from baseline summaries/listings are combined into a single display.

^[2]: Adverse events potentially related to autoimmunity will be identified via checkbox on the eCRF, "In the opinion of the investigator, is this an autoimmune event?".

9.2.1 Longitudinal Sustained Engraftment and WASP expression

Longitudinal sustained engraftment is defined as the percentage of lentiviral vector (LVV) transduced-colony forming units (CFU) in bone marrow cells (%LVV in BM) over time. WASP expression is described in Section 9.1.3⁹ will be analysed over the whole phase of follow-up.

The longitudinal profile of the transduced cell evaluation in BM and PB over time will be described by means of a listing and a plot.

The %LVV in BM over the time course of the study will also be plotted.

The longitudinal profile over time of WASP expression will be described with a listing for qualitative results from Western Blot if available; and a figure for quantitative results from flow cytometry, as described in Section 9.1.3.

Individual profiles of bone marrow and peripheral blood immunophenotype data will be presented over time in line plots. Listings will be created of bone marrow morphology and karyotype data, bone marrow blood count and immunophenotype data, peripheral blood immunophenotype data, peripheral blood immunophenotype subpopulations outside the normal reference range, serum immunoglobulin data and lymphocyte proliferative response.

9.2.2 Sustained Multilineage Engraftment of Genetically Corrected Cells in Peripheral Blood and Bone Marrow

Adequate engraftment of genetically corrected cells in peripheral blood and/or in bone marrow is defined in Section 9.1.2 and will be analysed over the whole follow-up phase. Adequate engraftment for further subpopulations than BM CD34+ and PB CD3+ will be defined as ≥ 0.04 VCN/cell.

A summary table detailing the number and percentage of subjects who present adequate engraftment each year after gene therapy will be generated, with the 95% CI of the percentage calculated.

The summary statistics and the longitudinal profile of the genetically corrected cells over time will be described by means of a listing and a plot together with BM CD34+ and PB CD3+ as described in Section 9.1.2.

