4.3.2. Secondary efficacy endpoints

a) *Longitudinal analyses of sustained engraftment of genetically corrected hematopoietic stem cells in peripheral blood and/or in bone marrow and expression of vector derived WASP*

Presence of gene corrected cells and WASP expression will be assessed at the time points shown in [Table 8a](#) and [Table 8b](#), as described above.

b) Analyses of sustained multilineage engraftment of genetically corrected cells in peripheral blood and/or in bone marrow

Presence of gene corrected cells assessed by quantitative PCR on all the available peripheral blood and/or bone marrow cell subpopulations (BM subpopulations: GlyA+, CD15+, CD3+, CD19+, CD56+; PB subpopulations: CD15+, CD19+, CD56+) at 1, 2 and 3 years after gene therapy. The availability of all the subpopulations depends on the amount of samples and on the technical procedures.

Adequate engraftment is defined as ≥0.04 VCN/cell (equivalent to 4% assuming a VCN of 1).

c) *Reduced frequency of severe infections*

Decrease in number of severe infections as evaluated starting from the first year follow up visit and thereafter until the 3-year visit after the treatment, by , complete physical examinations, hematological and microbiological tests compared to clinical history from the 12 months prior to GT. Infections will be assigned a CTCAE grading (as described in Section [4.3.2.1](#)) by the Investigators, identical to how severity grading was used in clinical history.

d) *Reduced bleeding episodes*

Reduction in bleeding manifestations when present, as assessed starting from the first year follow up visit and thereafter until the 3-year visit, by clinical monitoring, compared to clinical history from 12 months prior to GT. Information about bleeding will be recorded through follow up by collecting data from parents, clinical reports periodically sent by local doctors following the patients at home and by clinical evaluations performed at each follow up visit at our center. Data will be recorded in the patients' clinical charts. Bleeding events will be given CTCAE grading (as described in Section [4.3.2.1](#)) by the Investigators, identical to how severity grading was used in clinical history.

e) *Reduced autoimmunity phenomena and eczema*

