8.4.2. Abnormal clonal proliferation (ACP)

For safety monitoring of abnormal clonal proliferation, the following plan will be implemented during the first 3 years of follow up:

- A. First level screening (*every 6 months*)
 1. Clinical evaluation
 2. Blood count with differential to detect abnormal proliferation or cytopenia
 3. Routine biochemical tests to detect abnormal organ functions
 4. Serum immunoglobulins and protein serum electrophoresis, for the presence of altered or monoclonal immunoglobulin components
 5. Flow cytometry on peripheral blood for lymphocyte subpopulations (CD2, CD3, CD4, CD8, CD56, CD16, TCR alfa/beta, TCR gamma/delta, CD19, Ig-kappa, Ig-lambda)
 6. Flow cytometry with monoclonal antibodies for TCR Vbeta families
 7. PCR analysis for measuring vector copy number (VCN).
- B. Second level screening (*every year*):
 1. Bone marrow aspirate, including morphological examination, cytogenetic analysis and detailed immunophenotyping
 2. Cytogenetic analyses on lymphocytes (karyotype)

3. Archive pellets and viable cells of BM and/or PB.
- C. Additional tests (if above tests suggest monoclonal expansion, to be performed on recent and archived samples):
 1. BCR clonality (PCR)
 2. Clonality analysis for TCR (PCR)
 3. Establishment of cell lines
 4. Molecular tests for identifying proviral integrants ((Linear-amplification mediated) LAM-PCR or (ligation-mediated) LM-PCR)
 5. RT-PCR for expression of vector and genes next to the integration
 6. All other appropriate imaging and laboratory tests.

Tests (1) to (5) are available as research grade at TIGET

Test of first and second level screening (I, II) are already included in the efficacy evaluation in [Table 8a](#) and [Table 8b](#).

For the long-term follow up (from 3 years up to 8 years) the ACP safety-monitoring tests will be performed as follows:

- 1) First level screening will be performed every year from the 4th to 8th year of follow up.
- 2) Second level screening will be performed as follows:
 - a. Bone marrow aspirate on *year 5 and 8*
 - b. Cytogenetic analyses on lymphocytes (karyotype): every year from the 4th to 8th year follow up
 - c. Archive pellets and viable cells of BM and/or PB: every year from the 4th to 8th year follow up

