9. ASSESSMENT OF EFFICACY

9.1. Sustained engraftment of genetically corrected cells in peripheral blood and/or in bone marrow

Positive engraftment will be assumed as detectable gene corrected cells on peripheral blood and bone marrow cells at 1 year after gene therapy. Adequate engraftment is defined as $\geq 4\%$ CD34+ cells (equivalent to 0.04 VCN/cell) in the bone marrow or $\geq 10\%$ peripheral blood T lymphocytes or peripheral blood mononuclear cells (when cells are not sufficient) (equivalent to 0.1 VCN/cell). This value is based on clinical experience in other gene therapy trials, which has demonstrated 4% average long-term engraftment of autologous hematopoietic stem/progenitor cells transduced with retroviral vectors in the bone marrow of paediatric patients with ADA-SCID and receiving reduced intensity, non-myeloablative conditioning ([Aiuti et al., 2009](#); unpublished results).

To further confirm results, the PB T cell or PB MNC cells and the pre-GT sample will be performed at MolMed S.p.A.

In addition, the multilineage engraftment will be evaluated in BM and/or PB subpopulations (BM subpopulations: GlyA+, CD15+, CD3+, CD19+, CD56+; PB subpopulations: CD15+, CD19+, CD56+). If data on PB CD3+ are not available, the average of PB CD4+ and PB CD8 T cells will be calculated and reported as T-cell engraftment. Adequate multilineage engraftment is defined as $\geq 4\%$ in all the available cells (equivalent to 0.04 VCN/cell).

Assessment parameter: PCR for transduced cells (specific for lentiviral vector sequences).

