The percentage of subjects who present at one year after gene therapy with adequate multilineage engraftment defined as $\geq 4\%$ in bone marrow and in peripheral blood cell subpopulations (BM subpopulations: GlyA+, CD15+, CD3+, CD19+, CD56+; PB subpopulations: CD15+, CD19+, CD56+) will be estimated and the 95% Confidence Intervals (CI) of this proportion will also be calculated.

A descriptive analysis of the other secondary efficacy endpoints will be provided.

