9.1.1 Overall Survival

Overall survival is defined as the time in days from gene therapy to date of death. Subjects alive at the end of follow-up or having not yet reached the defined follow-up phase will be censored at the latest time point for which vital status information is available. Follow-up will be defined as all data up to the data cut or end of study depending upon availability of data per patient.

The Kaplan-Meier estimate of survival for the entire duration of follow up will be obtained, with 95% confidence interval (CI) if there is any fatal event. The analysis results will be presented in a graph as well as a table. A listing of fatal events will be reported as a safety display.

9.1.2 Engraftment of genetically corrected hematopoietic stem cells in peripheral blood and/or in bone marrow

Adequate engraftment of genetically corrected cells in peripheral blood and/or in bone marrow is defined as ≥ 0.04 VCN/cell in bone marrow CD34 $^{+}$ or ≥ 0.1 VCN/cell in peripheral blood T Lymphocytes CD3 $^{+}$ at 1 year after gene therapy.

Missing PB CD3 $^{+}$ values will be imputed using the mean PB CD4 $^{+}$ and PB CD8 $^{+}$ values obtained from the same sample at that visit. If insufficient data are available to determine an adequate engraftment, the response will be set to missing. This includes two scenarios:

- Neither BM nor PB samples provides data for engraftment assessment;
- Values are below the threshold for the respective sample matrix (BLQ).

A summary table detailing the number and percentage of subjects who present with adequate engraftment at 1 year after gene therapy will be generated, with the 95% CI of the percentage calculated. PCR transduced cell evaluation in BM and PB will be summarised with descriptive statistics and graphs. Time to adequate engraftment will be plotted and listed based on VCN in BM and PB. The percentage of lentiviral vector (LVV) transduced colony forming units (CFU) in bone marrow cells (%LV in BM) will also be tabulated and plotted.

The longitudinal profile of the PCR transduced cell evaluation in BM and PB over time will be presented in a listing and a plot.

A box plot will be created for engraftment (PB CD3⁺ and BM CD34⁺ VCN/cell) by treatment source (BM or PB) at each year post gene therapy.

Scatterplots will be presented of treatment dose (CD34+/kg), busulfan dose (AUC), and age at treatment against engraftment (PB CD3⁺ and BM CD34⁺ VCN/cell) at each year post gene therapy.

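### SAP 9.2.2 omits the protocol's rule that every available lineage must reach 0.04 VCN/cell, so the percentage of subjects with multilineage engraftment has no definition that matches the protocol

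*SAP*

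**What the plan says.** **Protocol.** Section 9.1 sets the multilineage threshold at 4% or more "in all the available cells (equivalent to 0.04 VCN/cell"). Section 12.4 turns this into an estimate with a 95% CI: "The percentage of subjects who present at one year after gene therapy with adequate multilineage engraftment defined as" at least 4% in marrow and in blood subpopulations. It names eight: marrow GlyA+, CD15+, CD3+, CD19+ and CD56+, and blood CD15+, CD19+ and CD56+. Section 4.3.2 b gives the same threshold and lineages at years 1, 2 and 3. There, the word *all* describes what is measured: "Presence of gene corrected cells assessed by quantitative PCR on all the available peripheral blood and/or bone marrow cell subpopulations". The same item warns that "The availability of all the subpopulations depends on the amount of samples and on the technical procedures".

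**SAP.** Section 9.2.2 is headed as sustained multilineage engraftment. Its first sentence says that adequate engraftment "is defined in Section 9.1.2 and will be analysed over the whole follow-up phase". Section 9.1.2 is the primary rule: marrow CD34+ of at least 0.04 VCN/cell "or ≥ 0.1 VCN/cell in peripheral blood T Lymphocytes". The next sentence of 9.2.2 sets 0.04 VCN/cell for subpopulations other than those two. The section then promises the number and percentage of subjects with adequate engraftment each year, with a 95% CI. Appendix 1 lists this output as Table 14.2.2.1.1, whose title refers to subjects with adequate multilineage engraftment. SAP 14, the summary of changes, does not mention the definition.

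**The concern.** The protocol has a combining rule and the SAP does not. SAP 9.2.2 gives a cut-off for each lineage and promises one percentage of subjects, without the step that turns several lineage results into one subject result. The only combining rule within reach is the either/or rule of 9.1.2, and it uses two populations outside the protocol's list of eight.

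This matters because of what the endpoint is meant to show. Protocol 1.1.6.2 expects corrected T cells to gain ground mainly by peripheral expansion. Protocol 1.1.5 reports that persistent thrombocytopenia after transplant went with low myeloid chimerism, and attributes this to the lack of selective advantage in the myeloid compartment. Correction in blood T cells alone is therefore weak evidence of multilineage correction. If the combining rule is left open until the final tables are programmed, it can be chosen with the results in view.

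**Working it through.** The plan gives no figure to reproduce: the sample of 8 is a feasibility number, and the endpoint is not powered.

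**1. The texts side by side**

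| Element | Protocol 9.1 / 12.4 | SAP 9.2.2 |
|---|---|---|
| Lineages | Eight named (5 marrow, 3 blood) | Not listed |
| Cut-off | 0.04 VCN/cell | 9.1.2 for marrow CD34+ and blood CD3+; 0.04 for the rest |
| Combining rule | All available | None; the cited 9.1.2 is either/or |
| Timing of the estimate | Year 1 (4.3.2 b assesses years 1, 2, 3) | Each year |
| Declared as a change | – | No |

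**2. One constructed patient (assumed values).** Blood CD3+ 0.50, marrow CD3+ 0.30, marrow CD34+ 0.02, and the other seven listed lineages between 0.01 and 0.03.
- Either/or rule of SAP 9.1.2: 0.50 ≥ 0.1, so adequate.
- Protocol rule: 1 of 8 listed lineages reaches 0.04, so not adequate.
- SAP 9.2.2 read lineage by lineage: adequate in marrow CD3+ only, with no subject-level result.

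**3. Weight of one patient.** 100/8 = 12.5 points. Wilson 95% interval, with p = x/n, n = 8, z = 1.96: [p + z²/2n ± z√(p(1−p)/n + z²/4n²)] / (1 + z²/n).
- 8/8 = 100% (67.6 to 100.0)
- 7/8 = 87.5% (52.9 to 97.8)
- 6/8 = 75.0% (40.9 to 92.9)

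**4. How far apart the two rules could be (illustration).** The documents give no pass rates, so these are assumptions. Let each lineage pass with probability p, with a common latent normal factor and correlation ρ. Given the factor z, the pass probability is q(z) = Φ[(Φ⁻¹(p) − √ρ·z)/√(1−ρ)]. All eight pass with probability E[q⁸]; either of two passes with probability 1 − E[(1−q)²]. At ρ = 0 and p = 0.90 these are 0.9⁸ = 0.430 and 1 − 0.1² = 0.990.

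| p | All eight, ρ = 0 | All eight, ρ = 0.8 | Either of two, ρ = 0 | Either of two, ρ = 0.8 |
|---|---|---|---|---|
| 0.80 | 16.8% | 58.7% | 96.0% | 87.1% |
| 0.90 | 43.0% | 75.5% | 99.0% | 94.4% |
| 0.95 | 66.3% | 86.0% | 99.8% | 97.5% |
| 0.99 | 92.3% | 96.4% | 99.99% | 99.6% |

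At p = 0.90 the gap is 99.0 − 43.0 = 56.0 points if lineages are independent, and 94.4 − 75.5 = 18.9 points at ρ = 0.8. It shrinks as p approaches 1.

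**5. A trap in the repair.** Marrow is scheduled at years 1, 2 and 3. After that, Protocol 8.4.2 places it at years 5 and 8 only, and the schedule in SAP Appendix 3 agrees. If the all-available rule is simply placed on the SAP's yearly table, years 4, 6 and 7 rest on three blood lineages. At p = 0.90, three pass in 0.9³ = 72.9% (ρ = 0) to 82.8% (ρ = 0.8), against 43.0% to 75.5% for eight. The series would rise by 7.3 to 29.9 points with no biological change.

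**The case against.** The strongest reply is that SAP 9.2.2 never says a T-cell-only patient counts as multilineage engrafted. Its second sentence keeps the 0.04 cut-off for every further subpopulation. Appendix 1 also lists a CD34+/CD3+ table (14.2.1.2.1) separate from the multilineage table, and reusing the either/or rule would make the second largely repeat the first. Lineage-by-lineage reporting is the more natural reading. SAP 8 also leaves table content to a shells document that is not available here.

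That stands against the stronger reading that the SAP has replaced the all-lineages rule with an either/or rule. A reader might infer this from the cross-reference, but the text does not prescribe it. It does not rescue the endpoint, because lineage-by-lineage reporting yields no subject-level percentage across lineages, and that is what Protocol 12.4 asks for. An endpoint definition belongs in the SAP rather than in table shells.

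A reader might also infer that the planned yearly series is already distorted at years 4, 6 and 7. The documents do not support that. The protocol sets this endpoint at years 1, 2 and 3, when marrow is taken, and the SAP's yearly table has no all-lineages rule. The shift arises only if the two are combined carelessly.

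It is also true that harm is limited. The endpoint is secondary and descriptive, and its intervals are nominal. VCN summaries, median and individual VCN plots by lineage, the VCN listing and the percentage of transduced marrow colonies would all still show a T-cell-only pattern.

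**Conclusion.** The point holds as a conflict between protocol and SAP over an endpoint definition. The protocol's subject-level rule is missing from SAP 9.2.2, the omission is undeclared, and neither available reading of the SAP gives the protocol's percentage. Counting a patient corrected only in T cells is something the wording fails to exclude, and no more than that.

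The firm size is 12.5 points for each reclassified patient out of 8. The comparison of 43% to about 75% with 94% to 99% rests on an assumed 90% pass rate and latent correlations of 0 to 0.8. It shows that the rules can differ materially and does not predict this trial's data. This should be corrected before the final analysis, but no primary conclusion depends on it.

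**What to change.** In SAP 9.2.2:
- Replace the cross-reference to 9.1.2, as the responder rule, with a statement that a subject is a multilineage responder if every available listed subpopulation is at least 0.04 VCN/cell, and list the eight. Keep the protocol's limit to available lineages.
- Report the number of lineages available per subject. Show subjects with missing lineages separately or in a sensitivity count, because the rule is easier to pass when fewer lineages are assayed.
- Give the full marrow-plus-blood composite only at marrow visits (years 1, 2, 3, 5 and 8), and a blood-only composite (CD15+, CD19+, CD56+) every year. Identify year 1 as the estimate that Protocol 12.4 specifies.
- Keep the percentages for each lineage as supportive, and record the clarification in SAP 14.

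The cost is a wording change and derived flags from data already collected. The downside is that the reported percentage may be less favourable.

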9.2.3 Frequency of severe infections

Severe infections will be recorded on the Relevant Medical History page, Concomitant Diseases page and Adverse Event page. Severe infections will be identified as infections and infestations graded CTCAE 3 or above. The CTCAE pre-defined criteria are specified in the protocol. Severe infections, unless otherwise stated, will be summarised according to the phases in which the event started. Terms that will be considered as infections are defined in [Appendix 2](#). The number of severe infections will be evaluated comparing post-treatment phases vs. pre-treatment phases as defined in Table 4. Severe infections occurring in the first 12 months prior to gene therapy will be considered for the pre-treatment comparison.

A tabulation of the severe infection events by System Organ Class and Preferred term will be presented. The rate of infections will be estimated pre- and post- treatment as the number of any severe infections per person-year. The number and percent of subjects with severe infections, and the number of severe

infections will be summarised by means of a table and a plot by treatment phase. A listing of all severe infections will be produced.

9.2.4 Bleeding episodes

Bleeding will be recorded on Relevant Medical History page, Concomitant Diseases page and Adverse Event page. Terms that will be considered for bleeding episodes are defined in [Appendix 2](#).

Bleeding episodes will be summarised and listed in the same way as severe infections.

A separate table and plot will be produced to summarise the bleeding episodes by severity and by SOC. Three severity categories will be used for the table: Mild for CTCAE grade 1, Moderate for CTCAE grade 2, and Severe for CTCAE grade 3 or above.

Summaries of severe bleeding events and moderate bleeding events will be created. Each summary will compare the pre-gene therapy phase with the post-gene therapy phase. Rate of events per patient year outcome will be presented along with accompanying confidence interval. A separate summary of the number and rate of bleeding events defined from Haemorrhages (SMQ) will be presented, by treatment phase and severity. All bleeding episodes will be listed.

A plot of the distribution of bleeding events by site (SOC) will be presented as pie charts representing each of the treatment phases defined in Table 2.

9.2.5 Autoimmunity Phenomena

For pre-treatment, autoimmunity events will be determined from a manual review of medical history; additional data will be retrieved from the eCRF for AEs pre-GT (since AEs were not collected pre-GT).

Adverse events related to autoimmunity are identified by the investigator on the eCRF.

Modification of autoimmunity will be evaluated starting from the first year follow-up visit and at day 180 then every year after gene therapy until final assessment (where data are available) and compared to clinical history. Subjects with positive autoimmunity laboratory tests will be listed and summarised over time.

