16.3 Safety

16.3.1 Tables

Number	Title	Analysis Set
14.3.1.1.1	Summary of AEs NCI CTCAE \geq 2 and Laboratory Features NCI CTCAE \geq 3 During the First 100 Days after Gene Therapy by SOC and Preferred Term	MS
14.3.1.2.1	Summary of Number of Subjects with an SAE within 48 Hours from Infusion by SOC and PT	MS
14.3.1.3.1	Summary of Subjects with Positive Replication Competent Lentivirus (RCL) Results	MS
14.3.2.1.1	Summary of Subjects with Positive Immune Response to Transgene	MS
14.3.2.2.1	Summary of Number of Subjects with Adverse Events by Treatment Phase	MS
14.3.2.2.2	Summary of All Adverse Events by SOC, Preferred Term and Treatment Phase	MS
14.3.2.2.3	Summary of Related Adverse Events by SOC, Preferred Term and Treatment Phase	MS
14.3.2.2.4	Summary of Serious Adverse Events by SOC, Preferred Term and Treatment Phase	MS
14.3.2.2.5	Summary of Unexpected Adverse Reactions by SOC, Preferred Term and Treatment Phase	MS [1]

Commentato [MS1]: Removed as it is not in TOC

14.3.2.2.6	Summary of Suspected Unexpected Serious Adverse Reactions by SOC, Preferred Term and Treatment Phase	MS [1]
14.3.2.2.7	Summary of All Adverse Events by Severity (Grade), SOC, Preferred Term and Treatment Phase	MS
14.3.2.2.8	Summary of Grade 3, 4, and 5 Adverse Events - 12 Months Pre- vs. Post-Gene Therapy	ITT [2]
14.3.2.2.9	Number and Rate of Most Frequently Reported Adverse Events (Rate \geq 1 per PYO in Any Treatment Phase) by Preferred Term	MS
14.3.2.2.10	Number (%) of Subjects with Autoimmunity Adverse Events of Special Interest by Preferred Term and Treatment Phase	MS
14.3.2.2.11	Summary of Adverse Events by Preferred Term, Ordered by Decreasing Frequency	MS
14.3.2.2.12	Number (%) of Subjects with Immune Mediated Adverse Events by Preferred Term and Treatment Phase	MS
14.3.2.2.13	Number (%) of Subjects with Eczema and Dermatological Adverse Events by Preferred Term and Treatment Phase	MS
14.3.2.2.14	Number (%) of Subjects with Autoimmunity Adverse Events based on Dictionary Defined Terms by Preferred Term and Treatment Phase	MS
14.3.2.3.1	Summary Statistics for Laboratory Parameters	MS
14.3.2.3.6	Summary of Shifts from Baseline to Maximum and Minimum Values for Lab Parameters	MS
14.3.2.3.7	Summary of Laboratory Data Relative to Normal Range Over Time	MS
14.3.2.3.8	Summary Statistics for Immunoglobulins	MS
14.3.2.4.1	Summary Statistics for Vital Signs	MS

[1] Added for final analysis

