	Kaposi's varicelliform eruption Limbal swelling Lip oedema Lip swelling Mast cell degranulation present Medical device site dermatitis Medical device site eczema Medical device site hypersensitivity Medical device site rash Medical device site recall reaction Medical device site urticaria Mouth swelling Mucocutaneous rash Multiple allergies Nephritis allergic Nikolsky's sign Nodular rash Oculomucocutaneous syndrome Oculorespiratory syndrome Oedema mouth Oral allergy syndrome Oropharyngeal blistering Oropharyngeal spasm Oropharyngeal swelling Palatal oedema Palatal swelling Palisaded neutrophilic granulomatous dermatitis Palpable purpura Pathergy reaction Periorbital oedema Pruritus allergic Radioallergosorbent test positive Rash Rash erythematous Rash follicular Rash generalised Rash macular Rash maculo-papular Rash maculovesicular Rash morbilliform Rash neonatal Rash papulosquamous Rash pruritic
--	---

	Rash pustular Rash rubelliform Rash scarlatiniform Rash vesicular Reaction to azo-dyes Reaction to colouring Reaction to drug excipients Reaction to preservatives Red man syndrome Scrotal oedema Serum sickness Serum sickness-like reaction Skin necrosis Skin reaction Skin test positive Solar urticaria Solvent sensitivity Stevens-Johnson syndrome Stoma site hypersensitivity Stoma site rash Swelling face Swollen tongue Toxic epidermal necrolysis Toxic skin eruption Type I hypersensitivity Type II hypersensitivity Type III immune complex mediated reaction Type IV hypersensitivity reaction Urticaria Urticaria cholinergic Urticaria chronic Urticaria contact Urticaria papular Urticaria physical Urticaria pigmentosa Urticaria vesiculosa Vaccination site dermatitis Vaccination site eczema Vaccination site exfoliation Vaccination site hypersensitivity Vaccination site rash Vaccination site recall reaction Vaccination site urticaria
--	---

	Vaccination site vasculitis Vaccination site vesicles Vaginal exfoliation Vaginal ulceration Vasculitic rash Vessel puncture site rash Vulval ulceration Vulvovaginal rash Vulvovaginal ulceration
Autoimmunity	Investigator decision on eCRF page

18 Appendix 3: Schedule of Events

Pre and post-treatment evaluation (up to 36 months after gene therapy)

Parameter	Time point																								

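### Clinical autoimmune events are found by one method before gene therapy and another after it, then compared with no shared case definition or look-back window

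*SAP*

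**What the plan says.** Protocol 4.3.2(e) defines the endpoint as a fall in laboratory markers, clinical manifestations of autoimmunity, or both, judged against clinical history.

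**Before gene therapy.** SAP 9.2.5 says: "For pre-treatment, autoimmunity events will be determined from a manual review of medical history". The sentence goes on to a second source: "additional data will be retrieved from the eCRF for AEs pre-GT (since AEs were not collected pre-GT".

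**After gene therapy.** The same section says: "Adverse events related to autoimmunity are identified by the investigator on the eCRF". Footnote 2 to SAP Table 8 gives the form: "Adverse events potentially related to autoimmunity will be identified via checkbox on the eCRF". The box asks for the investigator's opinion. SAP Appendix 2, which lists terms for infections, bleeding and eczema, has a single entry for autoimmunity: "Investigator decision on eCRF page".

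**The comparison.** Autoimmunity is evaluated at day 180 and year 1, "then every year after gene therapy until final assessment (where data are available) and compared to clinical history". SAP Table 8 plans a change-from-baseline summary for it.

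**Other planned displays.** The safety list in SAP 16.3.1 has a table of autoimmunity events (14.3.2.2.10), one of immune-mediated events (14.3.2.2.12), and 14.3.2.2.14: "Number (%) of Subjects with Autoimmunity Adverse Events based on Dictionary Defined Terms by Preferred Term and Treatment Phase". The only autoimmunity table in the efficacy list (14.2.2.3.1) counts subjects with a positive laboratory test.

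**The concern.** A before/after contrast in a single-arm trial can be read only if events are found in the same way on both sides. Here someone reads the history for one period, and the investigator answers a question about each adverse event in the other. The plan does not say who reads the history or by what criteria. It does not say how far back the history goes, or which of the displays carries the clinical half of the endpoint. With no control arm, this contrast is the trial's only evidence on whether clinical autoimmunity falls, and a difference in breadth between the two methods cannot be told apart from a change in the disease.

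**Working it through.** The plan gives no effect size, power or error rate for this endpoint, so there is no figure to reproduce. The check is mainly textual.

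**1. Autoimmunity against its sister endpoints**

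| Feature | Severe infections, bleeding (SAP 9.2.3, 9.2.4) | Clinical autoimmunity (SAP 9.2.5) |
|---|---|---|
| Case definition | Appendix 2 terms | History review before; investigator opinion after |
| Source pages | Relevant Medical History, Concomitant Diseases, Adverse Event | Medical history plus retrieved eCRF data before; adverse events after |
| Pre-treatment window | Days -365 to -1 (SAP Table 3) | None stated |
| Rate per person-year | Planned | Not planned |

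For infections the SAP is explicit: "Severe infections occurring in the first 12 months prior to gene therapy will be considered for the pre-treatment comparison". Protocol 4.3.2(c) and (d) also require infections and bleeds to be graded in the same way as in the history. Item (e), on autoimmunity, has no such clause.

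**2. Does Table 14.3.2.2.14 already supply a common definition?** Not as written, for three reasons.
- SAP 10.2.2.3 says a MedDRA list will identify each event type and points to Appendix 2, which contains no autoimmunity terms.
- The table is a safety display on the Mobilisation Set, while secondary efficacy uses the ITT set (SAP 9.2). Nothing names it as the endpoint analysis.
- It is tabulated by treatment phase. For adverse events those phases come from SAP Table 2, whose pre-treatment phase opens at screening, so the clinical history before screening falls outside it.

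**3. A related inconsistency.** SAP 9.2.5 says adverse events were not collected before gene therapy, while SAP 10.2.2 says they are recorded from screening. Protocol 8.2.3 sends events between enrolment and infusion to the Concomitant Diseases page.

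**4. Illustration on assumed figures only.** Suppose treatment changes nothing, and each affected patient is detected with probability s_pre before and s_post after. The apparent ratio of affected patients is then s_post / s_pre, and the expected counts are 8 × p × s. For p, take the two cohort incidences in protocol 1.1.3.4, 40% and 72%. The chance of an apparent fall is the exact probability that fewer patients are detected after than before, with independent detection, summed over the binomial number truly affected.

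| s_pre / s_post | Ratio | Expected counts, p = 0.40 | Expected counts, p = 0.72 | Chance of apparent fall (0.40; 0.72) |
|---|---|---|---|---|
| 1.00 / 1.00 | 1.00 | 3.20 → 3.20 | 5.76 → 5.76 | 0%; 0% |
| 0.95 / 0.70 | 0.74 | 3.04 → 2.24 | 5.47 → 4.03 | 58%; 77% |
| 0.90 / 0.80 | 0.89 | 2.88 → 2.56 | 5.18 → 4.61 | 37%; 51% |
| 0.80 / 0.90 | 1.12 | 2.56 → 2.88 | 4.61 → 5.18 | 14%; 17% |
| 0.70 / 0.95 | 1.36 | 2.24 → 3.04 | 4.03 → 5.47 | 5%; 4% |

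The sensitivities are invented. The table shows only that unequal detection moves the result either way. One patient of 8 is 1/8 = 12.5 percentage points.

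**The case against.** The strongest reply is that the plan is nearer to a common method than SAP 9.2.5 suggests. SAP 10.2.2.1 builds the adverse event tables from all three record pages. It also plans a preferred-term listing that covers autoimmunity, to be read alongside a manual search, so manual search is not confined to the pre-treatment period. SAP 10.2.2.3 promises term lists from the dictionary current at reporting. On this view only a list and a sentence are missing. Part of this stands: the ingredients exist, which is why the change is cheap. But SAP 9.2.5 states a different rule for each period and then compares the results, and a listing for review is not a case definition.

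A second reply is that a term list is not plainly better. Protocol 1.1.1 notes that platelet destruction in this disease may be intrinsic or autoimmune, so a coded term may need clinical judgement. That stands, and is the reason to keep the checkbox table.

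Three stronger readings are tempting, and the documents support none of them.
- That the whole endpoint is compromised. The autoantibody tests are scheduled at baseline and after treatment, and the laboratory summaries do not depend on how clinical events are found.
- That the bias favours the product. An unblinded investigator might under-call events, but a question asked for each adverse event could also catch more than a retrospective history does.
- That two written definitions conflict. Neither side has written criteria, and the same investigators might judge both. What differs is the method of ascertainment.

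**Conclusion.** The concern holds for the clinical-event component only. Events are found by history review plus retrieved eCRF data before gene therapy and by an open-label investigator checkbox after it. They are then compared without a shared case definition or a stated look-back window, and the dictionary table does not cure this as specified. Any difference in breadth between the methods would pass for a treatment effect, in a direction and to an extent that the documents do not determine.

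The consequence is limited to interpretation. The endpoint is secondary and descriptive in an unpowered study of 8 patients (SAP 6 and 7; protocol 12.4), so no error rate, sample size or decision rule depends on it. It is a cheap improvement.

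**What to change.** - Add a fixed MedDRA preferred-term list for autoimmunity to SAP Appendix 2, as SAP 10.2.2.3 already promises.
- Apply it identically to the Relevant Medical History, Concomitant Diseases and Adverse Event pages.
- Extend SAP Table 3 to autoimmunity, comparing the 12 months before gene therapy with the post-treatment phases. The SAP now reserves that table's windows for displays of other data, so this needs a sentence. Say also how a condition that began before the window and is still present is counted, because the severe-infection convention counts by onset.
- Report number of subjects and rate per person-year in the ITT set, and name this as the before/after analysis of clinical autoimmunity.
- Keep the investigator-checkbox table as supportive and post-treatment only.
- Reconcile SAP 9.2.5 with SAP 10.2.2 on whether adverse events were collected before gene therapy.

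**Cost.** One term list, an efficacy table and SAP wording. Medical history and adverse events are already to be MedDRA-coded (SAP 8.3, 10.2.2), and the adverse event tables already draw on all three pages, so no new data are needed. The downside is that a term list may miss or misclassify events that need clinical judgement; for the post-treatment period the supportive table still shows the investigator's view.
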